## iii. Treatment Phase

- a. **INCLUSION Criteria:** After the washout phase, the following are requirements a subject must meet in order to be considered for enrollment into the treatment phase of the study:
  1. After the six-week washout phase, the subject continues to meet all screening and washout inclusion/exclusion study criteria
  2. After the six-week washout phase, subject's Baseline (Visit 2) IOP measured between 8:00 and 10:00 AM, is between  $\geq 23$  and  $\leq 34$  mmHg in at least one eye
  3. Subject's Baseline (Visit 2, morning average) IOP is  $\geq 5$  mmHg from the subject's SCREENING (pre-washout) IOP in at least one eye whose Baseline IOP is between  $\geq 23$  and  $\leq 34$  mmHg
  4. Investigator is able to dilate the lower puncta of each eye to 1.0 mm, and insert a study plug into each puncta.
- b. **EXCLUSION Criteria:** If any of the below criteria apply to a study subject that has completed the washout period, the subject does not qualify for enrollment into the treatment phase of the study:
  1. A subject who no longer meets all the screening and washout study criteria
  2. A subject who cannot be successfully inserted with a Travoprost Evolute® in the lower puncta of each eye, even if only one eye qualifies for enrollment.

**STUDY VARIABLES:** The following will be performed and/or recorded during the course of the study:

- a. Obtain written HIPAA and Informed Consent
- b. Verify a subject has not used any hypotensive ocular drops within the last 12 hours prior to the screening visit or at any time during the washout or treatment phases of the study
- c. Record any changes in the subject's use of any concomitant medications or ocular drops, gels or ointments during the course of the study
- d. Record subject's demographic data and medical history for past 6 months

- e. Perform a urine pregnancy test on a female subject of child-bearing potential at their screening and last study visits
- f. Measure subject's temperature, heart rate and blood pressure
- g. Record subject's Best-Corrected (Glasses) Distance or Pinhole Visual Acuity
- h. Verify documented automated perimetry results have been measured in the last 6 months  
**NOTE:** If perimetry measurement are older than 6 months, perform automated perimetry at the screening visit.
- i. Verify corneal thickness measurements are documented in the subject's chart  

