### 5.2.1.1 Screening Phase - Inclusion Criteria

The following are requirements a subject must meet in order to be considered for inclusion into the study screening phases of the study:

1. Male or female subject, 18 years of age or older at the time of the screening examination and has been diagnosed with bilateral OAG or OH
2. A subject must be able and willing to read, comprehend and give Authorization for Use/Disclosure of Health Information (HIPAA) and informed consent
3. A subject must not have taken any ocular hypertension medication(s) within 12 hours of the screening visit
4. A subject must be willing to have the lower puncta of each eye inserted with a study plug
5. A subject's screening visit (pre-washout) IOPs, measured between 8:00 and 10:00 AM, is less than 22 mmHg in both eyes
6. A subject IOPs are currently controlled (< 22 mm Hg) with a topical prostaglandin or in conjunction with one other topical ocular hypotensive drug, not including any fixed-combination formulations (i.e., Cosopt, Combigan, Azarga, etc.), in both eyes for at least one month
7. A subject must be willing to comply with study instructions and agree to complete the entire course of the study
8. A subject must agree to make all office appointments and have all office visits occur between 8:00 and 10:00 AM
9. Women of child-bearing potential must not be pregnant or lactating, must have a negative pregnancy test at screening and must be practicing an adequate method of birth control, including intrauterine device (IUD); oral, dermal ("patch"), implant or injected contraceptives; tubal ligation; or barrier methods with spermicide
10. A subject has a Best-Corrected Distance (Glasses), pinhole visual acuity of 20/100 (Snellen) or better in both eyes
11. A subject has documented perimetry results within the last 6 months prior to the Screening Visit for both eyes

**NOTE:** If perimetry measurement are older than 6 months, perform automated perimetry at the screening visit

12. A subject has documented central corneal thickness measurements between >500 µm and <600 µm in both eyes

**NOTE:** if corneal thickness data is not available, measure corneal thickness of each eye using pachymetry at the screening visit

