### 5.2.3 Study Treatment Phase Criteria

#### 5.2.3.1 Treatment Phase - INCLUSION Criteria:

After the washout phase, the following are requirements a subject must meet in order to be considered for enrollment into the treatment phase of the study:

- 1) After the six-week washout phase, the subject continues to meet all screening phase inclusion/exclusion criteria
- 2) After the six-week washout phase, subject's Baseline (Visit 2) IOP, measured between 8:00 and 10:00 AM, is  $\geq 23.0$  and  $\leq 34.0$  mmHg in at least one eye

- 3) Subject's Baseline (Visit 2, morning average) IOP is  $\geq$  5 mmHg from the subject's SCREENING (pre-washout) IOP in at least one eye whose Baseline IOP is between  $\geq$  23 and  $\leq$  34 mmHg.
- 4) Investigator is able to dilate the lower puncta of each eye to 1.0 mm, and insert a study plug into each puncta.

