#### 5.4.2.2 Reasons for Disqualification

A study subject will be disqualified from the study if there was a failure to obtain written informed consent or HIPAA Authorization, improper entry (did not meet all study inclusion/exclusion criteria), had a positive pregnancy test (at Visit 1).

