### 7.2 Study Procedures/Evaluations

#### 7.2.1 Study Specific Procedures

Procedures that are required during the course of the study include ([Appendix C](#) for details):

- a. Informed consent and HIPAA authorization: The Investigator and or qualified staff will review and answer any questions a potential study subject may have regarding the study, the consent or HIPAA authorization forms. Prior to the initiation of any study specific activities, the subject must sign both documents
- b. WOMEN OF CHILDBEARING POTENTIAL, urine pregnancy tests are required at the screening visit and when the female subject exits the study
- c. Record subject's demographic data and medical history for the previous 6 months

- d. Concomitant Medication use: All prescription systemic, ophthalmic and over-the-counter concomitant medications that will be used by the study subject will be documented. The medication name, start and stop dates, indication, dose, route of administration and any dosing alterations during the study period must be documented on the Concomitant Medications CRF
- e. Verify a subject has followed all instructions regarding the discontinuation of any hypotensive ocular medication during the course of the study
- f. Vital Signs (Temperature, Blood Pressure and Heart Rate): Throughout the study vital signs will be taken with the subject in the sitting position after the subject has rested five minutes. Techniques used to collect vital signs should remain consistent throughout the study
  - Temperature maybe taken using a non-contact (Infrared) thermometer or orally. Oral temperatures should not be taken within five minutes of ingestion of any food or drink
  - Blood pressure may be determined manually with a blood pressure cuff and auscultation or with an automated Blood Pressure monitor
  - Heart rates may be determined electronically with an automated Blood Pressure monitor. Manually obtained heart rates should be recorded after a minimum of 30 seconds of observation.
- g. Best-Corrected Distance Visual Acuity testing: Visual acuity with correction (e.g., wearing glasses) will be measured using a Snellen chart. Pinhole visual acuity will be measured using a Snellen chart while the subject is looking through a pinhole occluder. The test distance and lighting conditions specified for the Investigator's chart must be used and kept constant throughout the study

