#### 7.4.3.6 Visit 7 - Day 90 ± 7, Post-Plug Insertion (Final Study Visit)

At this visit the following will be performed and recorded:

- a. Verify a subject has not used any hypotensive ocular drops since his/her last visit
- b. Record any addition, discontinuation or changes in the subject's use of any concomitant medications or ocular drops, gels or ointments since his/her last visit
- c. If performed at SCREENING Visit, perform a urine pregnancy test on a female subject of child-bearing potential
- d. Record subject's temperature, heart rate and blood pressure
- e. Record subject's Best-Corrected (Glasses) Distance or Pinhole Visual Acuity
- f. Evaluate the position of each Travoprost Evolute using the slit-lamp prior to removal of the plug
- g. Perform a slit-lamp examination of each eye prior to study plug removal
- h. Record IOP measurement for each eye before study plug removal

- i. Removal of the study plug from each eye (refer to [Section 6.1.7](#) for details regarding removal of a punctal plug)
- j. Record any reported Adverse Events/Adverse Device Event

An exit form will be completed at the final study examination (Visit 7), or whenever the study subject completes or leaves the study for any reason.

**NOTE:** The day each Travoprost Evolute® are removed with no addition follow-up required, will be the study subject's official exit date from the study. However, **if the subject is exiting from the study due to an AE/SAE or ADE/SADE, the study subject will be followed and exam findings recorded by the investigator until the AE/SAE or ADE/SADE has resolved or has become medically stable.**

Schedule of Assessments, Events							
Visit Examination Parameters	Visit 1 Screening	Visit 2 (Day 0)	Visit 3 (Day 1)	Visit 4 (Day 7)	Visit 5 (Day 28)	Visit 6 (Day 60)	Visit 7 (Day 90)
Informed Consent/HIPAA	1						
Medical Hx (past 6 months)/Demographic Data	1	2 A					
Urine Pregnancy Test (Only women of childbearing potential)	1 B						7 B
Concomitant Med Use	1	2	3	4	5	6	7
BT (temperature), BP (blood pressure), HR (heart rate)	1	2	3	4	5	6	7
Evaluate study plug position prior to any eye exam		2*	3	4	5	6	7
Best-Corrected Distance (Glasses) or Pinhole VA	1	2	3	4	5	6	7
Automated Perimetry (Not required if measured in last 6 months)	0						
Pachymetry (Not required if documented in patient's chart)	0						
Slit-Lamp Examination	1	2	3	4	5	6	7
IOP (Goldmann) Evaluation (To be measured between 8 and 10 am)	1	2	3	4	5	6	7

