## **8 USE IN SPECIFIC POPULATIONS**

### **8.1 Pregnancy**

#### Risk Summary

There are no adequate and well-controlled studies in pregnant women to inform a drug-associated risk.

In animal reproduction studies, subcutaneous (SC) administration of travoprost to pregnant mice and rats throughout the period of organogenesis produced embryo-fetal lethality, spontaneous abortion, and premature delivery at potentially clinically relevant doses.

Advise pregnant women of a potential risk to a fetus. Because animal reproductive studies are not always predictive of human response, TRAVATAN Z should be administered during pregnancy only if the potential benefit justifies the potential risk to the fetus.

The background risk of major birth defects and miscarriage for the indicated population is unknown; however, in the U.S. general population, the estimated background risk of major birth defects is 2% to 4% and of miscarriage is 15% to 20% of clinically recognized pregnancies.

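### No pregnancy test is scheduled on the day of plug insertion, so an unrecognised pregnancy conceived during washout could be exposed to travoprost until the exit test

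*Combined protocol and SAP*

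**What the plan says.** Section 7.2.1, item b, sets the timing: "WOMEN OF CHILDBEARING POTENTIAL, urine pregnancy tests are required at the screening visit and when the female subject exits the study". The Synopsis, Study Variables item e, says the same: "Perform a urine pregnancy test on a female subject of child-bearing potential at their screening and last study visits". Both copies of the Schedule of Assessments mark the pregnancy-test row at Visit 1 and Visit 7 only. Key B ties the exit test to a test having been done at screening. Sections 7.4.1 and 7.4.3.6 list the test. Section 7.4.3.1 (Visit 2), the lists for Visits 3 to 6 and Section 7.5 (unscheduled visits) do not.

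Eligibility is to be re-established after washout. Section 5.2.3.1, item 1, requires: "After the six-week washout phase, the subject continues to meet all screening phase inclusion/exclusion criteria". Section 7.4.3.1, item b, tells the site to check for changes in medical history and to confirm all criteria at Visit 2. Screening inclusion criterion 9 in Section 5.2.1.1 is among them: "Women of child-bearing potential must not be pregnant or lactating, must have a negative pregnancy test at screening". The same criterion requires adequate contraception.

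On hazard, the Appendix J label says that travoprost given to pregnant mice and rats "produced embryo-fetal lethality, spontaneous abortion, and premature delivery at potentially clinically relevant doses".

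**The concern.** The test is placed at a visit where no study drug is given and is absent from the visit where exposure begins. Criterion 9 has three parts: not pregnant or lactating, a negative test at screening, and contraception. The screening result settles the second part for good. The first describes a state that can change during six weeks, and the plan asks the site to confirm it on the day of insertion without a test. IOP, visual acuity and slit-lamp findings are all measured again that day.

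The main stake is fetal exposure in a pregnancy that nobody has recognised. A smaller one concerns the data. A woman already pregnant at insertion would have entered in breach of Section 5.2.3.1, and Section 10.1 allows subjects with entry-criterion violations to be excluded from the primary analysis.

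**Working it through.** The plan states no figure for these intervals, so the check is calendar arithmetic on its own schedule.

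1. **Screening test to first exposure.** Washout is six weeks (Section 7.4.2): 6 × 7 = 42 days. No window is given for Visit 2, so 42 is nominal.
2. **First exposure to next scheduled test.** Visit 7 is Day 90 ± 7 (Section 7.4.3.6): Day 83 to Day 97. Under Section 7.6, early exit brings the Visit 7 procedures, including the test, forward.
3. **Interval between tests for a completer.** 42 + 83 = 125 days; 42 + 90 = 132 days; 42 + 97 = 139 days.
4. **Duration of drug release.** Section 6.1.4 gives a load of 166 µg and a rate of 1 to 2 µg per day. At 1 µg/day a plug lasts 166 / 1 = 166 days; at 2 µg/day, 166 / 2 = 83 days. Release to Day 97 needs a constant rate of at most 166 / 97 = 1.71 µg/day, which is inside the stated range. Day 97 is therefore possible but is an upper limit. Near the top rate a plug would be empty earlier, unless it had been replaced.
5. **How long a pregnancy would have to go unnoticed.** A conception at the end of washout followed by a Day 83 test gives 83 days. One at the start followed by a Day 97 test gives 42 + 97 = 139 days. That is about 12 to 20 weeks after conception.
6. **Expected number.** The documents give no contraceptive failure rate. As an assumption only, take 1% to 13% per year. The chance of conceiving in 42 days is 1 − 0.99^(42/365) = 0.12% to 1 − 0.87^(42/365) = 1.6% per woman. If 3 of the treated subjects were women of childbearing potential (also an assumption), the expected count of washout conceptions is 0.003 to 0.05. If all 30 were, it is 0.03 to 0.48. Unrecognised pregnancies are a subset of these.
7. **Hazard in the labels.** Rat malformations were seen at 10 µg/kg/day, given as 250 times (Appendix I), 60 times (Appendix J) and 1500 times (Appendix K) the maximum recommended human ocular dose. Appendix J also reports adverse pregnancy outcomes in rats from 0.12 µg/kg/day, or 0.7 times that dose by estimated Cmax, with a no-effect level at 0.6 times.

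**The case against.** The strongest reply is that the pregnancy-test passages all agree, so this is a design choice with several safeguards around it. Contraception is an entry condition. Visit 2 includes a history check and a full eligibility check. Visits 3 to 6 include a medication review, and every study visit includes a standard question about problems. Early exit triggers the test. Entry requires current use of a topical prostaglandin, so the drug class is not new to these women. The malformation doses are far above human exposure, and the Appendix J and K labels list no contraindications and allow use in pregnancy when benefit justifies risk. Appendix K gives a mean age of 65 years (range 21 to 92) in its trial in this indication, so few women of childbearing potential are likely.

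Most of this stands, and it limits the size of the problem. It does not supply the missing check. History and questions find recognised pregnancies only, and the Appendix J findings at 0.7 times the human dose mean the hazard cannot be dismissed on dose multiples alone.

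Three stronger readings are tempting and are not supported:

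- A reader might infer from Section 5.4.2.2, which names a positive test at Visit 1, that a positive result at Visit 2 would have no consequence. The same sentence also disqualifies for improper entry. Section 5.2.3.2, exclusion 1, bars a subject who no longer meets the screening criteria, and the note in Section 7.4.3.1 discontinues her.
- A reader might infer that Section 8.5 treats a later pregnancy merely as a protocol deviation. It also requires the investigator to inform the Sponsor and to collect follow-up on the pregnancy, the birth and the child. It provides special CRFs, and follow-up continues after site close-out.
- A reader might infer that any woman who conceives in washout receives 97 days of drug. That needs an unrecognised pregnancy, no early exit, a Visit 7 at the end of its window, and a release rate that lasts until then.

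**Conclusion.** The gap is real and narrow. The plan asks for confirmation of non-pregnancy at Visit 2 and schedules no test to support it. An unrecognised pregnancy conceived during the nominal 42-day washout could be exposed from insertion until as late as Day 97.

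The intervals rest only on the plan's schedule. The expected number rests on assumed failure rates and an assumed count of eligible women, and it is very small for a trial of up to 30 subjects. Replacement of discontinued subjects could raise the number treated somewhat above 30 without changing that conclusion. The case for acting rests on the low cost of closing the gap before first exposure, not on a likely event. It is an inexpensive improvement to the schedule and leaves the IOP analysis as planned.

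**What to change.** Add the urine pregnancy test already used in the study to the Visit 2 column of both Schedules of Assessments and to the list in Section 7.4.3.1, for women of childbearing potential. The result should be read before dilation and insertion. Align Section 7.2.1 item b, Synopsis item e and key B.

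The Visit 1 wording in Section 5.4.2.2 may be aligned for consistency, but this is optional because other provisions already cover a positive result at Visit 2. Separately, Sections 5.4 and 8.5 should be reconciled on participation after a pregnancy is found: pregnancy found after insertion is not a named exit reason in Section 5.4, and Section 8.5 does not address participation or the plugs. What that rule should be is for the sponsor.

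The cost is one urine test per eligible woman at a visit that already takes place, a few minutes at Visit 2, and an occasional late screen failure.

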**Keys to Abbreviations:**

- A = Verify no change in medical history, subject still meets all study inclusion/exclusion criteria
- B = If performed at the screening visit, must be performed when subject exit the study
- C = In a subject where both eyes qualified at Visit 2, if a plug is extruded in one eye, **plug is to be replaced** and subject continues in the study
- D = In a subject where only one eye qualified at Visit 2, if the plug is extruded in the qualified eye, the subject will be DISCONTINUED and replaced. In a subject where both eyes qualified, if a plug is extruded in one eye, then extruded again or in the fellow eye, the subject will be DISCONTINUED and replaced
- \* = Plug position evaluated after eye exam and plug insertion
- ‡ = If subject EXITs the study after visit 2, but before visit 7, subject must return to Investigator's office to have plugs removed

Body Temperature:	Temperature maybe taken using a non-contact (Infrared) thermometer or orally. Oral temperatures should not be taken within five minutes of ingestion of any food or drink
Heart Rate:	Heart rate taken in the sitting position after subject has rested for 5 minutes. Recorded values can be obtained electronically (automated) or manually (observed for 30 seconds or more)
Blood Pressure:	Blood pressure, taken in the sitting position after subject has rested for 5 minutes. Recorded values can be obtained electronically (automated) or manually
Plug Position Evaluation:	Position of the plug will be evaluated as either: Normal, Present but requires adjustment, Extruded/Recovered, Extruded/Lost, Other
Slit-Lamp Exam:	Evaluation will include the Lids (Upper & Lower), Conjunctiva (Bulbar & Palpebral) and the Cornea. SL Findings will be graded on a 5-point scale: 0 = None, 1 = Trace, 2 = Mild, 3 = Moderate, 4 = Severe
IOP Evaluation:	Goldmann applanation tonometry will be used for measuring IOP. Just prior to the start of the study, the tonometer should be calibrated. IOP of each eye will be measured twice, alternating between the eyes. The average of the two measurements will be used for analysis. However, if there is a $\geq 3$ mmHg difference between the 1 st and 2 nd measurement for an eye, a 3 rd measurement will be taken and the average of the two closest values of the three will be used for analysis for that eye.

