- h. Automated Perimetry (visual fields) will be measured using a Humphrey's Visual Field Analyzer (manufactured by Carl Zeiss Meditec Inc., Dublin, CA) with at least a standard full-threshold 24-2 program or Swedish interactive threshold algorithm (SITA) program. **Visual fields measured and documented up to SIX months before the Screening Visit are acceptable** to fulfill the screening criteria
  - i. Pachymetry can be measured by contact methods, such as ultrasound and confocal microscopy (CONFOSCAN), noncontact methods such as optical biometry with a single Scheimpflug camera (such as SIRIUS or PENTACAM), dual Scheimpflug camera (such as GALILEI), or Optical Coherence Tomography (OCT), such as Visante. **Past corneal thickness measurement documented in the subject's chart** are acceptable to fulfill the screening criteria
  - j. Slit-Lamp Examination: Examination will include assessment of the lid, conjunctiva and cornea. Grading of slit-lamp findings are defined in [Appendix C](#).
  - k. Perform a NON-DILATED fundus exam of each eye. Using an ophthalmoscope, the investigator will examine the back part of the eye (fundus), including the retina, optic disc, choroid and blood vessels and evaluation of the lens
  - l. Goldmann applanation tonometry will be used for measuring IOP. IOPs will be measured in the morning between 8:00 and 10:00 am. The IOP of each eye will be measured twice, alternating between the eyes. However, if the second measurement is  $\geq \pm 3$  mmHg from the first measurement for an eye, a third measurement will be taken. All measurements taken will

be recorded. In the case of two measurements, the average of the two values will be used for analysis, and in the case of three measurements, the average of the two closest values of the three will be used for analysis for that eye at that specific time point.

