**“Have you had any problems since your last visit?”**

#### 7.2.2 Standard of Care Procedures

At any study visit (scheduled or unscheduled), in addition to study specific examinations the Investigator will perform their standard evaluations for an OAG or OH patient.

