Non-Dilated Fundus Examination (Include evaluation of the LENS)	1						
Begin Six-Week Washout (D/C all topical drops, gels, ointments)	1						
Punctal Size Evaluation, Dilation of Lower Puncta		2					
Insertion of Punctal Plugs		2					
**Punctal Plug Extrusion			☆ C	☆ C,D	☆ C,D	☆ C,D	7
Removal of Punctal Plugs after eye exam completed†							7‡
Adverse Event/Adverse Device Event Recording		2	3	4	5	6	7

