##### Listing of Anticipated Ocular Adverse Events

###### DRUG:

Incidence rate 30-50%: Hyperemia (\*Hyperemia in IZBA controlled studies noted at 12%)

Incidence rate 5-10%: Decreased VA, Eye Discomfort, Foreign Body Sensation, Pain, Pruritus

Incidence rate 1-4%: Abnormal Vision, Blepharitis, Blurred Vision, Cataract, cells, Conjunctivitis, Corneal Staining, Dry Eye, eye disorder, Iris Discoloration, Keratitis, Lid Margin Crusting, Ocular Inflammation, Photophobia, Subconjunctival Hemorrhage, Tearing

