##### f. Evaluation of Slit-Lamp Findings (Lids, Cornea, Conjunctiva)

The severity of a sign will be graded by the investigator based on the appearance at each study visit using the following scale:

NONE (0) = Normal;

TRACE (1) = Slightly visible;

MILD (2) = Somewhat visible and diffuse;

MODERATE (3) = Visible and diffuse;  
SEVERE (4) = Extremely visible and dense

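### Anterior chamber and lens have no scheduled, graded assessment after plug insertion, although the protocol anticipates cells, ocular inflammation and cataract

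*Combined protocol and SAP*

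**What the plan says.** The content of the slit-lamp examination is described consistently in three places:

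- Section 7.2.1(j): "Examination will include assessment of the lid, conjunctiva and cornea".
- Notes to the Schedule of Assessments: "Evaluation will include the Lids (Upper & Lower), Conjunctiva (Bulbar & Palpebral) and the Cornea", graded 0 to 4.
- Appendix C(f), which defines the grades: "Evaluation of Slit-Lamp Findings (Lids, Cornea, Conjunctiva".

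The examination is scheduled at all seven visits. At the last it reads "Perform a slit-lamp examination of each eye prior to study plug removal".

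The lens appears once in the schedule, within another procedure marked at Visit 1 only: "Non-Dilated Fundus Examination (Include evaluation of the LENS". It is absent from the procedure lists for Visits 2-7. It is therefore also absent from the early exit visit (7.6), which repeats Visit 7, and it is not in the minimum set for an unscheduled visit (7.5).

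The 1-4% band in section 8.6.4 includes "Cataract, cells, Conjunctivitis, Corneal Staining, Dry Eye, eye disorder, Iris Discoloration" and, further on, ocular inflammation. Table 1 in section 2.3.1 lists cells, ocular inflammation, iris discoloration and cataract in the same band.

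Slit-lamp findings are a named safety variable in sections 4.2.3, 8.1 and 10.4.4. Section 7.2.2 adds that, at any visit, "in addition to study specific examinations the Investigator will perform their standard evaluations for an OAG or OH patient".

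**The concern.** Safety is in the study title and objective. Section 2.2 suggests that a continuous low dose might lessen ocular side effects, and section 2.3.1 allows that drug and plug together might bring risks not yet known. There is no control arm, so systematic observation at fixed visits is the main safeguard behind any safety statement.

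Followed exactly, the plan would produce a slit-lamp safety table with no rows for two structures in which the protocol itself expects events. A reader could take the absence of cells or lens change as evidence that they did not occur, when nobody was scheduled to look. A case found incidentally would also be hard to interpret: the anterior chamber has no recorded baseline, and the lens has a Visit 1 evaluation that is never repeated.

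**Working it through.** The documents give no power or sample-size figure on this point to reproduce (section 10.5 states that none was done). The check compares the texts, then gives the size under a stated assumption.

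**Anticipated event against scheduled assessment.** Visit 2 precedes insertion, so the post-insertion visits are Visits 3-7, five in all. Cells are read as anterior-chamber cells; Appendix I lists them near flare.

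| Event listed at 1-4% | Structure | Scheduled before insertion | Scheduled at Visits 3-7 |
|---|---|---|---|
| Cells | Anterior chamber | None | 0 of 5 |
| Cataract | Lens | Visit 1 only, in the fundus examination | 0 of 5 |
| Ocular inflammation, external | Lids, conjunctiva, cornea | Visits 1 and 2 | 5 of 5 |
| Ocular inflammation, internal | Anterior chamber | None | 0 of 5 |
| Iris discoloration | Iris | None | 0 of 5 |

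**Size.** Inputs: n = 30 subjects, the planned maximum (section 5.1), and incidence p of 1% to 4% (section 8.6.4). The 1-4% figures come from travoprost eye drops. That they apply to the plug is an assumption, as are independence between subjects and detection of every case by an examiner who looks.

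- Expected cases, n × p: 30 × 0.01 = 0.3; 30 × 0.04 = 1.2.
- Chance of at least one case, 1 − (1 − p)^n: 1 − 0.99^30 = 0.260; 1 − 0.96^30 = 0.706.
- One-sided 95% upper bound for 0 of 30 examined, 1 − 0.05^(1/30) = 0.095.

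So a given event has a 26% to 71% chance of occurring at least once. If all 30 were examined and none had it, rates above 9.5% would be excluded at that confidence level. That bound lies above the whole 1-4% range, so even a full examination could not show a rate as low as with drops. Without a scheduled examination the zero has no known denominator of subjects examined, and the 9.5% bound cannot be claimed either.

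**The case against.** The strongest reply is that the plan leaves several other routes to these data. Investigators perform standard evaluations at any visit (7.2.2). The adverse event definition covers signs as well as symptoms (8.2.1). Anticipated events need an adverse event form (8.6.4), and all events are reportable whatever their severity or attribution (8.7). Source documents must hold all relevant observations (11.1). Acuity at every visit is an indirect check on the lens. Nor does the wording of 7.2.1(j) forbid noting other findings.

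This stands as far as it goes. A reader might infer that there will be no follow-up data at all on these structures, that effects would surface only through complaints, or that asymptomatic cases would almost never be found. The documents support none of these: incidental data can arise, and nothing in them quantifies detection.

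The routes do not close the gap, however. The content of the standard evaluations is unspecified and may differ across up to 8 sites, with no grading. The visit question depends on the subject noticing something. The adverse event form applies only once someone has seen the event, and 8.2.1 words an adverse event as unanticipated, which leaves some doubt about anticipated signs. Snellen acuity says nothing about cells.

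Three further points narrow the claim:

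- Iris colour carries little weight. Section 2.3.1 says change may take months to years to be noticed, treatment lasts 90 days, and subjects enter already controlled on a topical prostaglandin.
- External inflammation is covered by the present grading.
- Cells appear in the incidence list of Appendix I but not in those of Appendices J and K, and chronic or recurrent inflammatory eye disease is excluded. Cells may therefore be uncommon here, although the protocol itself lists them.

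Finally, this is a small open-label pilot, the slit-lamp content is consistent throughout, and the primary IOP endpoint is untouched. That limits the priority of the point without removing it.

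**Conclusion.** The point holds in this form: after insertion, neither the anterior chamber nor the lens has a scheduled or graded assessment at any of the five visits, while the protocol anticipates cells, ocular inflammation and cataract. Capture rests on subject reports and on what investigators happen to note. A zero count would therefore not support a safety statement for these structures.

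The 26% to 71% range and the 9.5% bound give scale only. They rest on eye-drop rates carried over to the plug, on 30 treated subjects, and on complete detection when examined; the textual gap depends on none of these. The trial can run without the change, but its safety summary would be silent on structures where its own list places events. The change should be made.

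**What to change.** In section 7.2.1(j), the notes to both copies of the Schedule of Assessments, and Appendix C(f):

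- Add anterior-chamber cells/flare and an undilated lens assessment to the existing slit-lamp examination at Visit 2 (before insertion), Visits 3-7 and early exit.
- Give each a grading definition suited to it. The present 0-4 anchors describe how visible, diffuse or dense a sign is; they do not define cell or flare grades or lens opacity, and applying them unchanged would make grades hard to compare across sites.
- In section 10.4.4, state that shifts from Visit 2 will be tabulated with the number examined at each visit, so that a zero has a denominator.

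Iris colour is optional and of low yield at 90 days. While editing Appendix C, reconcile item h, which is headed as a dilated fundus examination and omits the lens, with the non-dilated examination including the lens in 7.2.1(k), 7.4.1 and the schedule.

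The cost is a few extra case report form items and slightly longer visits. No new equipment, visit, dilation or repeat fundus examination is needed, because the slit lamp is already used on both eyes at every visit.
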